### **B. Are pregnant women included in this research?**

Yes

### **C. Are breast feeding women included in this research?**

Yes

#### **Provide justification**

None of the study interventions pose a risk to pregnant women or breastfeeding mothers. We will ensure that IRB compliance and protection standards will be met.

## **METHODS AND PROCEDURES**

### **12. Methods and Procedures Applied to Human Subjects**

**A. Are there any evaluations or tests that will be performed for the purpose of determining subject eligibility which would not be routinely conducted as part of standard clinical care of the prospective subject?**

No

**B. Describe the research plan, including all procedures, interventions, evaluations and tests.**

**BounceBack Now:**

BBN was developed at the Medical University of South Carolina and [name] participated in the app development. UNMC does not have anything to do with the app development.

After consent has been completed a BHP will assist the participant in downloading BBN onto their smartphone device for Aim 2. The current BBN structure contains a brief assessment and multiple treatment components for disorders that are frequently associated with traumatic event exposure. A brief assessment based on the Kessler 6 will be completed, based on this assessment the participants are then guided to treatment recommendations with an interactive rationale for each treatment. Education/explanations are provided in written, spoken, and animated video formats. Given that each of these treatments may be beneficial for patients with subsyndromal or very minor symptoms, all patients are able to see and interact with all treatment components, but it is anticipated that BHPs will provide recommendations for the sections that will be most beneficial. The treatment components are each based on effective in-person interventions. These include behavioral activation (depression), Written Exposure Therapy, and Expressive Writing (PTSD), Cognitive Behavioral Therapy for Sleep, and Relaxation/Mindfulness (stress/anxiety). The corresponding app sections are titled Activate, Write, Sleep, and Coping Tools, respectively. Each of these sections contains education components and there is a separate education component for the app overall that can be found through the coping tools page. An overview of each treatment component and its designed target is included below in table format.

**BBN Component**  
Initial Assessment  
Relaxation/Mindfulness  
Behavioral Activation  
CBT for Sleep  
Writing Exposures  
Psychoeducation

**Function**  
Identify symptoms, direct to appropriate intervention  
Reduce mild symptoms of anxiety  
Reduce depression symptoms  
Increase sleep duration and efficiency  
Decrease trauma-related anxiety and avoidance  
Basic and disorder-specific mental health education

**Aim 1:** Participants will be recruited in one of two ways for aim one. The first is patients who present to their behavioral health care provider ([name] or [name]), will be offered the opportunity to participate in focus groups/one on one semi-structured interviews to review the BBN (Bounce Back Now) trauma app. The behavioral health providers (BHPs) will discuss the study and refer interested participants. For interested participants, the BHP will provide them with a QR code that links directly to a Redcap survey that first presents the description of the study and initial screening eligibility assessment. If requested, BHPs will assist participants in scanning the QR code to obtain the link to the study. Basic information about the study will be shown first and state that we are interested in learning about how to better use mobile apps to benefit care for trauma-related mental health concerns (phrased to participants as emotional or mental health problems related to extremely stressful or traumatic events). Eligible participants will be directed to a page where they can electronically complete the IRB-approved consent form via Redcap. On this page, participants will affirm that they have read and understood the consent form and agree to participate in order to proceed. If they indicate that they decline to participate, they will be directed to a page that thanks them for their time. Once they complete the consent form, the redcap survey will ask for contact information and their preferred method of being contacted by the research team (IE phone call, text message or email.)

The second way participants may volunteer for the study is through promotional materials placed within the clinic and via clinicaltrials.gov registry or UNMC research database. These approaches help ensure inclusive opportunities for interested participants who may have or may have previously had experienced trauma-related mental health concerns who are not actively receiving care from a BHP, as their perspectives on the use of the app would still help inform any future adaptations. The in-clinic promotional materials will contain basic information about the study (i.e., that they can help us improve mental health apps), contain the QR code that links to the Redcap information and screening page (which asks their age and if they are receiving care from the approved Fontenelle or Midtown locations), and contact information for the study team where they can reach out for any additional questions.

If the interested participant reaches out to a member of the research team through the clinical trials registry or UNMC research database via email as opposed to scanning a QR code the participant will be emailed the Redcap link which will contain the above described content in addition to resource materials.. The QR code and link for the participants recruited via flyers and trials registry will differ from the ones that BHPs will use to recruit. . This is done because these participants may not have an existing relationship with a BHP and may not currently be engaged in BH services. We therefore will present different information at the end of the screening and consent process to inform them that they may request BH services from their clinic and we will provide a list of BH resources that they may access if they would like to seek services for mental health. For all of the above recruitment methods, using the QR code and screening/consent/download link in this manner, helps reduce barriers to participation and simplifies the process of completing measures and accessing the application.

Educational materials for patients and Behavioral Health Providers (BHPs) for BBN in IPC will be developed.

[name] and her research assistants will present the educational materials and BBN in focus groups. We will conduct one focus group for behavioral health providers and one to two focus groups for patients or offer individual virtual meetings (in order to accommodate their schedule, we may need to have two separate focus group for patients or individual times to participants). Upon semi-structured interview or focus group, a member of the research team will review the consent form contained in the

Redcap survey and reconfirm that patient understands and wishes to proceed. The re-verification of this information will serve as verification of consent. (Electronic Consent). These focus groups may be conducted virtually (i.e., zoom call) or in-person. The focus group will last 30 - 60 minutes. Focus groups will focus on acceptability, feasibility, and usability of the materials and the education materials and the app.

At the beginning of the focus group the patients will be asked to download BBN on their smartphone device with the assistance of the research team, if they have not already done so. A basic tutorial of the BBN and the developed educational materials will be conducted/reviewed with the participants. After the tutorial and education has been provided the participants will be asked to try some of major features of the app. Then, they will be asked to review the patient education materials. They will be asked to discuss strengths and weaknesses of the materials. They will be also asked whether there is any content missing from the education material. Finally, they will be asked to assess usability of the material. At the completion of the focus group the research team will assist the participants in removing BBN from their phones.

As for the provider focus group, a similar process will be used to ask about the provider educational materials and patient educational materials. We will also collect the following information including gender, age, job, years in practice, and years at the clinic.

Focus groups will be audio recorded and a transcript will be prepared. Information obtained from the focus groups will be used to refine the patient and provider educational materials before we implement Aim 2 activities.

**Aim 2: Conduct a pilot trial of BBN for patients with trauma histories in an IPC setting**

[name], UNL Faculty will be the PI of record for the Bluestem Health Clinics, He currently provides patient care services at these locations in addition to overseeing the work of other BHPs at the identified Bluestem sites.

[name], UNMC faculty, will be the PI for the other sites.

Recruitment will take place in two ways:

**1.) Baseline**

Prior to engagement with the BBN application and as part of standard care at the clinic, a primary care provider at one of the specified Fontenelle, Downtown, Midtown or Bluestem Clinic locations will do a standard "warm handoff" referral to a behavioral health provider (BHP) if the patient is determined to have a behavioral health issue. All participants under Aim 2 will have gone through this process and have discussed identified mental health needs with both the BHP and their primary care provider. They will therefore already be receiving behavioral health services. In this context, BHPs will advertise BBN and the study to participants they believe may benefit, which mimics naturalistic app recommendations in this setting. For such patients, the BHP will provide the patient with a QR code that directs participants to where they can download BBN, which is publicly available. Continuing further with standard care when using apps, BHPs will have discretion as to whom they will recommend BBN. All BHPs have been trained in its use and have viewed its functionality. They will then guide patients through the sections that they perceive as relevant for that patient. Any patient may be directed through these procedures regardless of whether they elect to participate in the research phase. Thus, all Aim 2 procedures to this point are for standard of care. However, they must have had BBN recommended to them by the BHP in order to be eligible for Aim 2 research. For any adult participants (i.e., 19+ years of age) to whom they introduce BBN, BHPs will be asked to advertise a research study on the use, perceptions and initial effectiveness of BBN. To do so, they will use flyers with a QR code that links to a Redcap survey. The BHP will inform the patient that participation in the

study is voluntary and does not affect their care or access to BBN. The BHP will also assist the patient with the QR code, if necessary, but it is anticipated that participants will interact with this link after the session has ended, which will reduce both patient and provider burden by minimizing disruption to services. The BHP will be trained to problem solve QR code usage with the patient to ensure they can access the link before leaving. The Redcap survey will begin with a modified consent form (it is modified in accordance with the prior waiver of written consent we received previously where participant will confirm the consent electronically). If participants agree to participate in the study, they will then complete a series of questionnaires. All questionnaires are standard in survey research and do not contain any items that identify risk or result in significant distress. They are listed under Research Assessment below. The measures do contain an assessment of stressful event exposure, but prior studies indicate that such measures do not significantly increase participant distress and more frequently report research studies involving such measure as a positive experience overall (Jaffe et al., 2015). Further, the consent procedures will explicitly suggest that participants complete the survey in a private setting and inform the participants that the study will contain questions about stressful life experiences. Additionally, participants will be afforded the opportunity to complete the study in a private setting at the clinic, though we anticipate some participants may choose to complete the survey after. They will be advised that they should complete the consent form and survey within two days of their appointment. At the end of the survey, they will be given information that they should reach out to their BHP if they would like to further discuss any symptoms or topics discussed during the assessment and that they may contact the research team with any questions about the study. The Redcap will also automatically redirect to a separate survey where participants can provide contact information for compensation and follow-up phone surveys (see Follow-up Phone surveys below). Participants will be able to provide contact information for compensation and still decline participation in follow-up phone surveys. Participants will also be able to indicate a preference for completing follow-up surveys electronically and receiving the link via email or text or completing the survey over the phone. They will be asked to provide the contact information corresponding with their preference.

The patient will continue to meet with their BHP as determined by the standard of care interactions. And, if deemed appropriate the BHP will highlight features contained in BBN for patient to use in between appointments.

2.) Recruitment for the study will occur in the manner described above in addition to this advertising opportunity to participate using Opt-in registry email which is described below. The opt in registry will be used to identify patients who meet the inclusion criteria and who have had an appointment with the BHP at one of the participating sites within the last three to six months. The Opt in email will provide basic information about the study and include a link which will take the interested participants to the same redcap survey described above which contains the informed consent, contact information for research team members for any questions prior to selecting to proceed, followed by research related questionnaires.

Participants choosing to participate with the Opt-in format will have already an established relationship with the BHP, documented trauma condition within the electronic health record and expressed interest in participating by proceeding from the opt-in initial inquiry. Upon completion of the initial baseline data collection from the participants, BHPs will made aware of the patients expressed interest through the opt-in recruitment process in order to incorporate the app use into subsequent standard of care appointments with the patient. This process will mimic the in-person appointments.

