**D. Describe the specific subject withdrawal criteria.**

Participants will be withdrawn if he/she voluntarily withdraws his or her consent to participate in a study at any time for any reason. Participants will also be withdrawn if any time they are experiencing any indication of suicidality and/or experiencing difficulty, either physically or mentally, with the study. Should this occur these events will follow the current

standard of care within their respective treatment facility.

**E. Describe the stopping rules for the research (e.g., the specific criteria for halting or early termination of the study).**

If for some reason the participant becomes upset during the interview, the qualitative researcher will bring the interview to the end, thank the participant for his/her participation and be available afterward to discuss any concerns participants may have. If 2 or more subjects become upset and require withdrawal from the trial, the trial will be halted.

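### Aim 2 opt-in patients consent and complete baseline before the behavioral health provider has confirmed the suicidality exclusion or recommended the app

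*Combined protocol and SAP*

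**What the plan says.** **Conditions for every Aim 2 patient.**
- Item 10 excludes patients with high suicidality and rests that judgment on the BHP's clinical assessment. It names no instrument and sets no limit on how old the assessment may be.
- The Baseline part of 12.B adds that "they must have had BBN recommended to them by the BHP in order to be eligible for Aim 2 research". It describes Aim 2 patients as coming through a primary care handoff to a BHP: "They will therefore already be receiving behavioral health services".

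**Visit route (12.B, recruitment way 1).** The BHP sees the patient, introduces the app, and then advertises the study. On timing, "They will be advised that they should complete the consent form and survey within two days of their appointment".

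**Opt-in route (12.B, recruitment way 2).** A registry search finds patients who meet the inclusion criteria and had a BHP appointment in the last three to six months. The exclusion criteria are not mentioned. An email links them to the same REDCap survey, which holds the consent and then the questionnaires. Once baseline is complete, the BHP is told of the patient's interest, so that app use can be built into later appointments.

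**After the survey.** On both routes, "they will be given information that they should reach out to their BHP if they would like to further discuss any symptoms".

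**Safety sections.** Under 18.D, "Participants will also be withdrawn if any time they are experiencing any indication of suicidality and/or experiencing difficulty", and such events then follow the "standard of care within their respective treatment facility". The prompt in 18.B asks who performs the ongoing data and safety analysis; the answer describes data security.

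**The concern.** On the visit route the order is sound: a BHP has just seen the patient, can apply the suicidality exclusion, and has recommended the app before the study is offered. On the opt-in route the BHP comes last. The two conditions that depend on BHP judgment are therefore neither selected for nor checked before the patient is consented and surveyed.

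Two things are at stake:
- **Safety.** A patient whose state has changed since the last appointment can enter although a current BHP assessment would have excluded them.
- **Eligibility and data.** A patient later found unsuitable by the BHP has already consented and supplied baseline data. With 15 patients planned, each such case is 1/15, or about 7%, of the Aim 2 patient sample.

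**Working it through.** The plan states no figure on this point, so none can be reproduced. The check compares the order of events on the two routes and then works out the size.

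**1. Order of steps (12.B)**

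| Step | Visit route | Opt-in route |
|---|---|---|
| How the patient is found | By the BHP at an appointment | By registry search on inclusion criteria and a past BHP appointment |
| BHP recommends the app | Before the study is offered | No step before baseline; app use is taken up at later appointments |
| BHP can apply the item 10 exclusion | At that appointment | No new step described before the link is used |
| Consent and baseline | After the BHP contact | Before the BHP is told |
| What the BHP learns | Already involved | The patient's interest, after baseline |

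**2. Could another section supply the missing step?**
- 12.A says no eligibility evaluation goes beyond routine care, so a new check cannot be assumed.
- 25.A.3 has an investigator with a clinical relationship or other legitimate access screen for eligibility. It does not say that this includes a current BHP suicidality assessment.
- 29.A requires patients to meet eligibility criteria before consent, and 29.D has BHPs identify eligible patients. Both are general statements. The opt-in text gives the specific order and places the BHP notice after baseline.

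**3. Age of the last BHP contact at baseline**
- Visit route: about 2 days, as advised.
- Opt-in route: the window is worded as three to six months, so both ends are shown. 3 × 365/12 = 91 days; 6 × 365/12 = 182.5, about 183 days.
- These are outer limits. An opt-in patient may have been seen more recently.

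**4. Number of patients.** Item 4 plans 15 Aim 2 patients. The split between routes is not given, so between 0 and 15 could enter by opt-in. The documents give no rate of suicidality, so the expected number wrongly admitted cannot be calculated.

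**The case against.** The best defense is that these patients are not strangers to the clinic. The Baseline text says all Aim 2 patients came through the handoff and are in behavioral health care, and the opt-in text says they have an established BHP relationship and a documented trauma condition. Ordinary appointments continue, and item 10 applies to everyone. What precedes the BHP notice is only consent and questionnaires, which the protocol says "do not contain any items that identify risk or result in significant distress". The study is classed as minimal risk. An earlier BHP assessment, or an earlier recommendation of the app, may well exist.

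Most of this stands, and it lowers the risk. It does not change the order: an earlier assessment may be months old, and the opt-in search neither looks for an earlier recommendation nor confirms one. Item 25.A.2 and the consent form were not available for this check. If either places a BHP confirmation before the link, the point falls away.

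A reader might infer more than the documents support, in three ways:
- **That the depression and PTSD questionnaires ought to trigger withdrawal under 18.D.** The documents show no suicidality item in the PROMIS depression form or the PCL-5. 18.D limits difficulty to difficulty with the study. BHP visits continue, and the PHQ-9 is listed as a standard clinical assessment. A high score is not the 18.D event, and compulsory score alerts would bring false alarms, new record linkage and possible under-reporting on outcome measures.
- **That the halting rule is undermined.** 18.E says "If 2 or more subjects become upset and require withdrawal from the trial, the trial will be halted", but it introduces this with a participant upset in an interview and does not count survey scores.
- **That opt-in patients have never been assessed.** The documents do not say so; what is missing is a current check before entry.

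**Conclusion.** The point holds for the Aim 2 opt-in route. As written, its sequence does not secure two conditions that the protocol itself sets: the suicidality exclusion resting on BHP assessment, and the BHP's recommendation of the app. The effect is limited to between 0 and 15 patients, with a last BHP contact up to about three to six months old.

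This rests on reading the opt-in paragraph as the operative order for that route, ahead of the general screening statements elsewhere. It needs no assumed event rate. It is an inexpensive improvement to safety and eligibility. It does not show that the study is unsafe or that its monitoring fails as a whole.

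A secondary and optional point is that 18.B leaves its question about safety analysis unanswered for Aim 2.

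**What to change.** Amend the opt-in paragraph of 12.B so that the treating BHP confirms that no item 10 exclusion applies, including high suicidality on a current assessment, and recommends the app before the baseline link is sent or opened. The email could ask for an expression of interest, with the link released once the BHP has confirmed.

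The fallback is to use the notice the BHP already receives after baseline, and to require the same confirmation then, before the patient continues in the study. This is weaker, because consent and baseline have already happened. The plan should then say how the baseline data of a patient found ineligible are handled.

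If the confirmation needs a contact outside routine care, the answer to 12.A must change too. Optionally, add a sentence to 18.B naming who reviews Aim 2 safety information.

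The cost is a short delay for opt-in patients and a small load on existing BHPs: at most 15 enrolled patients, plus any turned away. Checking everyone emailed, instead of those who respond, would mean more reviews, by a number the documents do not give.
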